## 6.6.3 Definition of Dose-limiting Toxicity

The DLTs will be evaluated during Part A Dose Escalation. The DLT evaluation period will be 28 days from the first dose of sabestomig on Cycle 1 Day 1. Participants who do not remain in the study for the entire duration of the DLT evaluation period, for reasons other than DLT, will be considered non-evaluable for DLT evaluation and will be replaced with another participant at the same dose level if needed to ensure a minimum of CCI evaluable participants in the ATD and mTPI-2 cohorts, respectively.

A DLT will be defined during Part A Dose Escalation as any  $\geq$  Grade 3 AE as per NCI CTCAE version 5 unless unequivocally due to underlying malignancy or an extraneous cause. The modifications and exceptions to this are detailed below.

The following conditions will be considered as DLTs:

- Any death not clearly due to the underlying disease or extraneous causes.
- Grade 4 imAE.
- Any  $\geq$  Grade 3 non-infectious pneumonitis irrespective of duration.
- Any  $\geq$  Grade 3 non-infectious colitis irrespective of duration.
- Liver transaminase elevation:
  - Isolated liver transaminase elevation > 5 x but  $\le 10$  x ULN that does not downgrade to AST/ALT  $\le 3$  x ULN or less within 7 days after onset with optimal medical management including systemic corticosteroids.
  - Transaminase elevation > 10 x ULN regardless of duration or reversibility.
  - Isolated TBL elevation > 3 x ULN that does not downgrade to ≤ 1.5 x ULN within 7 days after onset with optimal medical management (for participants with Gilbert's syndrome: TBL > 3 x ULN and doubling of direct bilirubin that does not downgrade to baseline value within 7 days).
  - Any increase in AST/ALT > 3 x ULN and concurrent increase in TBL  $\ge$  2 x ULN, regardless or duration or reversibility, where no other reason, other than the investigational product(s), can be found to explain the combination of increases (for participants with Gilbert's syndrome: TBL > 3 x ULN and doubling of direct bilirubin that does not downgrade to baseline value within 7 days).
- Any Grade 3 imAE, including rash, pruritus, or diarrhea (NOTE: this excludes colitis or pneumonitis, as these AEs are already defined above), that does not downgrade to Grade 2 or less within 7 days after onset of the event despite maximal supportive care including systemic corticosteroids.

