#### 6.6.8 Dose Modification and Toxicity Management

If a participant experiences a clinically significant and/or unacceptable toxicity including a DLT not attributable to the disease or disease-related processes under investigation, dosing will be interrupted, and supportive therapy will be administered.

All toxicities will be graded according to NCI CTCAE v5.0.

The following general guidance should be followed for management of toxicities:

- Treat each of the toxicities with maximum supportive care (including withholding the agent suspected of causing the toxicity if required).
- If the symptoms promptly resolve with supportive care, consideration should be given to resuming the assigned study intervention along with appropriate continuing supportive care. If medically appropriate, dose modifications (eg, dose interruption) are permitted.
- All dose modifications (eg, dose interruption, discontinuation) should be documented with clear reasoning and documentation of the approach taken.
- Dose reductions are not permitted.

Toxicity Management Guidelines have been developed to assist Investigators with the recognition and management of toxicities associated with use of the IC inhibitor sabestomig. The TMGs are provided in Appendix I.

These TMGs are applicable to the management of participants receiving sabestomig as specified in the CSP. The TMGs provide information for the management of immune-mediated reactions, IRRs, and non-immune-mediated reactions that may be observed with monotherapy or combination checkpoint inhibitor regimens, with specific instructions for checkpoint inhibitor-specific dose modifications (including permanent discontinuation) and treatment interventions. Investigators are advised however to use local practice guidelines and consult local references for the management of toxicities observed with other anticancer treatment.

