#### **Dosing Modification and Toxicity Management Guidelines (TMGs) for Sabestomig**

#### General Considerations Regarding Immune-Mediated Reactions

#### These guidelines are provided as a recommendation to support Investigators in the management of potential imAEs.

Immune-mediated events can occur in nearly any organ or tissue, therefore, these guidelines may not include all the possible immune-mediated reactions. Investigators are advised to take into consideration the appropriate practice guidelines and other society guidelines (eg, NCCN, ESMO) in the management of these events. Refer to the section of the table titled "Other -Immune-Mediated Reactions" for general guidance on imAEs not noted in the "Specific Immune-Mediated Reactions" section. Early identification and management of imAEs are essential to ensure safe use of the study intervention. Monitor patients closely for symptoms and signs that may be clinical manifestations of underlying imAEs. Patients with suspected imAEs should be thoroughly evaluated to rule out any alternative etiologies (eg, disease progression, concomitant medications, infections). In the absence of a clear alternative etiology, all such events should be managed as if they were immune-mediated. Institute medical management promptly, including specialty consultation as appropriate. In general, withhold investigational drug(s) for severe (Grade 3) imAEs. Permanently discontinue investigational drug(s) for life-threatening (Grade 4) imAEs, recurrent severe (Grade 3) imAEs that require systemic immunosuppressive treatment, or an inability to reduce corticosteroid dose to 10 mg or less of prednisone or equivalent per day within 12 weeks of initiating corticosteroids.

Based on the severity of the imAE, treatment with sabestomig should be withheld and corticosteroids administered. Upon improvement to Grade  $\leq 1$ , corticosteroid should be tapered over  $\geq 28$  days. More potent immunosuppressive agents such as TNF inhibitors (eg, infliximab) should be considered for events not responding to systemic steroids. Alternative immunosuppressive agents not listed in this guideline may be considered at the discretion of the Investigator based on clinical practice and relevant guidelines. With long-term steroid and other immunosuppressive use, consider need for *Pneumocystis jirovecii* pneumonia (PJP, formerly known as *Pneumocystis carinii* pneumonia) prophylaxis, gastrointestinal protection, and glucose monitoring.

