#### Management of immune-mediated liver injury caused by immune checkpoint inhibitors (ILICI)

Recommended management of treatment-emergent abnormal hepatic biochemical tests in clinical trials with sabestomig (patients with normal baseline ALT, ASTa)

Treatment Emergent ALT/AST	TBL b Values at Time of Treatment Emergent ALT Elevation	Investigational drugs treatment adjustment and additional therapy	Monitoring and evaluation
Normal	Isolated total blood bilirubin elevation > 3 × ULN	Discontinue investigational drug.	Repeat blood tests d within 2 to 3 days. Initiate close monitoring and evaluation e .
$\leq$ 3 x ULN	Normal. Patients with Gilbert's syndrome: No change in baseline TBL.	Continue treatment.	Repeat blood tests c within 1 to 2 weeks.
> 3 x ULN	Normal. Patients with Gilbert's syndrome: No change in baseline TBL.	Withhold investigational drug. If rising ALT/AST when re-checked, start prednisone/prednisolone 1 mg/kg/d f . If ALT/AST improve to $\leq 3.0$ x ULN, resume treatment after completion of steroid taper to equivalent of prednisone $\leq 10$ mg/day.	Repeat blood tests d within 2 to5 days. Initiate close monitoring and evaluation e .
	TBL $\geq 2 \times ULN$ . Patients with Gilbert's syndrome: Doubling of direct bilirubin.	Discontinue investigational drug. Start prednisone/prednisolone 1 to 2 mg/kg/d f .	Repeat blood tests d within 2 to 3 days. Initiate close monitoring and evaluation e .
> 5 x ULN	Normal. Patients with Gilbert's syndrome: No change in baseline TBL.	Withhold investigational drug. Start prednisone/prednisolone 1 to 2 mg/kg/d f . Resume treatment if elevations downgrade to AST and ALT $\leq 3.0$ x ULN within 14 days, and after completion of steroid taper to equivalent of prednisone $\leq 10$ mg/day. Otherwise discontinue investigational drug permanently.	Repeat blood tests d within 2 to 3 days. Initiate close monitoring and evaluation e . Treatment shall only resume following consultation with a hepatologist and based on a benefit/risk assessment for the affected participant.
> 10 x ULN	Normal or elevated.	Discontinue investigational drug. Start prednisone/prednisolone 1 to 2 mg/kg/d g .	Repeat blood tests d within 2 to 3 days. Initiate close monitoring and evaluation e .

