- b. Measurement of total and conjugated (or direct) bilirubin is recommended to help identify patients with indirect hyperbilirubinemia due to Gilbert's syndrome or hemolysis versus liver injury.
- c. Recommended blood tests include ALT, AST, ALP, GGT, TBL.
- d. Recommended blood tests include: ALT, AST, ALP, GGT, TBL, DBL, CK, INR.
- e. Initial monitoring should be 2–3 times a week. Frequency of monitoring may be adjusted based on clinical scenario and severity of injury. Monitoring should continue until ALT/AST levels return to  $\leq$  3 x ULN, regardless of whether or not the investigational drugs have been discontinued. For recommendations on diagnostic follow-up and evaluation of potential alternative etiologies see Table 1 below.
- f. Oral prednisone/prednisolone: if hepatic biochemical tests worsen on oral prednisone/prednisolone, change to IV (methyl)prednisolone. Once ALT/AST return to ≤ 3 x ULN, corticosteroids can be weaned over 2–4 weeks. Treatment with investigational drug(s) may be resumed with close monitoring, once prednisolone dose ≤ 10 mg/day.
- g. IV (methyl)prednisolone: if worsening continues on IV (methyl)prednisolone, consider adding MMF 500–1000 mg twice daily. Once hepatic biochemical tests return to Grade 1, corticosteroids can be weaned over 4 weeks. Treatment with investigational drug(s) may be resumed with close monitoring, once prednisolone dose ≤ 10 mg/day.
- Abbreviations: bsl: baseline; CK creatinine kinase; DBL direct Bilirubin; GGT Gamma-glutamyl transferase; INR international normalized ratio; IV: intravenous; PO: per os (taken orally); ULN upper limit of normal

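### Two rows of the Appendix I liver tables say to discontinue sabestomig, but the footnote marked only on those rows says it may be resumed

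*Protocol*

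**What the plan says.** Appendix I has two tables for immune-mediated liver injury, one for a normal and one for an abnormal baseline ALT/AST. The > 10 x ULN row of the first and the > 5 x baseline row of the second both read "Discontinue investigational drug. Start prednisone/prednisolone 1 to 2 mg/kg/d". Both carry footnote g, and neither states a condition for restarting.

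Footnote g covers IV steroid. It asks for liver tests to return to Grade 1 and then says "corticosteroids can be weaned over 4 weeks. Treatment with investigational drug(s) may be resumed with close monitoring", once prednisolone is 10 mg/day or less. It sets no time limit for recovery.

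The rows that foresee a restart use a different verb, Withhold, and give the conditions in the row. The > 5 x ULN row requires ALT/AST at or below 3.0 x ULN within 14 days and a steroid taper to 10 mg/day or less, then adds "Otherwise discontinue investigational drug permanently". Its monitoring column adds "Treatment shall only resume following consultation with a hepatologist and based on a benefit/risk assessment for the affected participant". The > 3 x baseline row has the same structure, with a target of 2 x baseline and the same 14 days, but no hepatologist step.

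**The concern.** An investigator whose participant reaches > 10 x ULN, or > 5 x an abnormal baseline, can follow the row and stop sabestomig for good, or follow the row's own footnote and re-dose. Both would be acting on the same page. The choice arises in the most severe transaminase rows of each table, where consistent handling matters most.

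Neither reading of the row leaves the text sound. If Discontinue is permanent, footnote g contradicts both rows that cite it. If it is temporary, the worst injuries would have no 14-day recovery limit, while the > 5 x ULN and > 3 x baseline rows do. They would also lack the hepatologist consultation that the > 5 x ULN row requires.

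**Working it through.** No arithmetic applies. The check is to set each row that starts a steroid beside its footnote, then look for a rule elsewhere that settles the matter.

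| Table | Row | Action | Footnote | Restart conditions in the row |
|---|---|---|---|---|
| Normal baseline | > 3 x ULN, normal TBL | Withhold | f | Yes |
| Normal baseline | > 3 x ULN, TBL >= 2 x ULN | Discontinue | f | None |
| Normal baseline | > 5 x ULN | Withhold | f | Yes; 14 days, hepatologist |
| Normal baseline | > 10 x ULN | Discontinue | g | None |
| Abnormal baseline | > 2 x baseline, normal TBL | Withhold | f | Yes |
| Abnormal baseline | > 2 x baseline, TBL >= 2 x ULN | Discontinue | f | None |
| Abnormal baseline | > 3 x baseline | Withhold | f | Yes; 14 days |
| Abnormal baseline | > 5 x baseline | Discontinue | g | None |

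**Count.** Footnote g is marked on 2 rows, both Discontinue, so its restart sentence is attached to no row that allows a restart. Footnote f is marked on 6 rows: 4 Withhold, where the same sentence fits, and 2 Discontinue.

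**Does another section decide it?**

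- *Section 6.1.2* requires, before each later cycle, that no Section 7.1 discontinuation criterion is met, that no permanent-discontinuation criterion is met, that Appendix I retreatment guidance is satisfied, and that Table 9 liver function is adequate (ALT/AST <= 2.5 x ULN, or <= 5 x ULN with liver involvement).
- *Section 7.1* speaks of permanent discontinuation, but says participants may be discontinued and refers back to Appendix I for the criteria. The reference is circular on this point.
- *Appendix I general rule*: "Permanently discontinue investigational drug(s) for life-threatening (Grade 4) imAEs, recurrent severe (Grade 3) imAEs that require systemic immunosuppressive treatment". The liver rows are set by multiples of ULN or baseline, not by grade, so the rule does not say that every event in these rows is permanent.
- *Section 6.6.3* lists "Transaminase elevation > 10 x ULN regardless of duration or reversibility" as a Part A DLT but states no drug action.
- *Section 6.6.8* points the other way in general terms: where symptoms settle promptly, "consideration should be given to resuming the assigned study intervention along with appropriate continuing supportive care".
- *12-week limits* (Section 6.7 on dose gaps; the Appendix I general rule on steroid reduction) bound the delay. They do not say whether a restart is allowed.

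**Could a footnote marker be wrong?** One marker looks odd: the blood tests in the > baseline row carry e where the matching normal-baseline row carries c. Exchanging f and g would not help, because both end with the same restart sentence.

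**The case against.** The strongest reply is that the body of the protocol already bars the next dose. A row saying Discontinue is most naturally an Appendix I discontinuation criterion, so Section 7.1 applies and the first condition of Section 6.1.2 fails. A permissive remark in a steroid footnote should not override that. This is probably what the sponsor intends, and it is why the fix goes in that direction. It does not close the point, because Section 7.1 is permissive and sends the reader back to the tables that disagree.

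A second reply is that footnote g hangs on the steroid dose, not on the drug action, and also reaches Withhold patients: footnote f says "if hepatic biochemical tests worsen on oral prednisone/prednisolone, change to IV (methyl)prednisolone". That may explain how the sentence got there. Those patients keep the restart conditions in their own rows, so they lose nothing if it is deleted.

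A third is that Appendix I describes itself as a recommendation. Section 6.1.2 nonetheless makes meeting its retreatment guidance a condition of dosing.

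A reader might also infer three stronger things, and the documents support none of them:

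- *That re-dosing after these events would face no enzyme threshold.* Table 9 applies before every cycle from the second onward, and footnote g requires Grade 1 before weaning.
- *That footnote g implies a recovery window in days to set against the 14.* It gives none. Deriving one from the 12-week limits needs assumptions about when the event and the taper fall. It would also compare return to Grade 1, whose ALT limits the documents do not state, with return to 3.0 x ULN or 2 x baseline.
- *That all four Discontinue rows in the table above are contradicted.* Footnote f fits the four Withhold rows it serves, so the two rows with TBL >= 2 x ULN are ambiguous rather than in clear conflict.

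**Conclusion.** The concern holds in a limited form. Two rows, which are all the rows carrying footnote g, give an instruction that their own footnote reverses, and no other section clearly says which prevails. Two further rows, with TBL >= 2 x ULN and footnote f, need clarification. Sections 6.1.2 and 7.1, Table 9, the Grade 4 rule and the 12-week limits leave a narrow gap: whether rechallenge is allowed at all after these events and, if so, with what recovery limit and specialist review.

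This is a minor documentation fault with a participant-safety consequence. Sample size, error rates and the efficacy analyses are untouched. The conclusion assumes the footnote markers are as they appear in the tables, but an exchange of f and g would not change it.

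**What to change.** In the Appendix I liver tables:

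1. Delete the last sentence of footnote g.
2. In the > 10 x ULN and > 5 x baseline rows, write *Permanently discontinue investigational drug*.
3. As a clarification, limit the last sentence of footnote f to rows that say Withhold, under the conditions in that row. State whether Discontinue is permanent in the two TBL >= 2 x ULN rows.

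If the sponsor does intend rechallenge after a Discontinue row, put the conditions in that row: recovery within 14 days, steroid taper to 10 mg/day or less, hepatologist consultation with a benefit/risk assessment, and the Table 9 liver limits that Section 6.1.2 already requires (ALT/AST <= 2.5 x ULN, or <= 5 x ULN with liver involvement). A separate 3.0 x ULN threshold should not be added, because it would be looser than Table 9 for participants without liver involvement.

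The cost is a few wording edits to two footnotes and up to four rows of one appendix. No laboratory threshold, visit or analysis changes.

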# Table 1 – Recommended evaluation of patients with treatment-emergent ALT elevation during a clinical trial with immune checkpoint inhibitorsa

Recommended evaluation	Competing causes of abnormal liver tests
1 st Line Testing	
Thorough history of symptoms, co-existing medical conditions, concomitant medications, dietary and nutritional supplements, excessive exercise or muscle injury, alcohol consumption, illicit substances.	Systemic infection/sepsis; ischemic/congestive hepatic injury; gallstone disease; alcoholic liver disease; muscle injury/rhabdomyolysis; acetaminophen toxicity; DILI due to another drug, herbal or dietary supplement.
Serum CK	Muscle injury/rhabdomyolysis b
Anti-HAV (IgM)	Acute HAV infection
HbsAg • Anti-HBc IgG, IgM, HBV DNA	Acute hepatitis B; Exacerbation of chronic hepatitis B
Anti-HCV	Acute hepatitis C
• HCV RNA (PCR)	Exacerbation of chronic hepatitis C c

Anti-HEV (IgG, IgM); HEV RNA d	Acute hepatitis E
ANA, ASMA • Quantitative immunoglobulins (IgG, IgM, IgA)	Autoimmune hepatitis e
Hepatobiliary imaging (ultrasonography, CT scan, MRI, MRCP) f	Biliary obstruction; pancreatitis; gallstones; portal-vein/hepatic vein thrombosis; hepatic metastasis
2 nd Line Testing	
Serological tests for EBV, CMV, HSV.	

 
May need to obtain acute and convalescent serological tests
 
EBV-DNA, CMV-DNA, HSV-DNA by PCR. Liver biopsy needed to confirm HSV
 
	Hepatic injury caused by CMV, EBV, HSV
Additional Tests g	
Anti-LKM-1	Autoimmune hepatitis
Serum EtOH	

 
Urinary ethyl-glucuronide and ethyl-sulfateh, Serum phosphatidylethanoli
 
	Alcohol related liver disease
Serum acetaminophen level; Acetaminophen protein adducts	Acetaminophen toxicity
Review of blood pressure, pulse, electrocardiogram, echocardiogram, cardiology consult	Ischemic or congestive hepatic injury
Urine toxicology screen	Hepatotoxicity due to cocaine, amphetamines, opiates and other illicit substances
Anti-HDV	Hepatitis D
Blood or urine cultures	Systemic infection, sepsis
Blood ceruloplasmin, serum copper	
• Slit lamp eye examination for Kayser-Fleischer rings, genetic testing	Wilson's disease

Abbreviations used: CMV, Cytomegalovirus; CK, creatine kinase; DILI, drug-induced liver injury; EBV, Epstein Bar Virus; HBV, hepatitis B virus, HbsAg, hepatitis B surface antigen; HCV, hepatitis C virus; HDV, hepatitis D virus; HEV, hepatitis E virus; HSV; Herpes Simplex Virus; LKM-1, liver kidney microsomal type 1.

#### Adapted from Arie Regev, et al., Journal of Autoimmunity, https://doi.org/10.1016/j.jaut.2020.102514

- a Extent and type of work-up may vary by patient's history, severity of liver injury, underlying disease, and geography.
- b Serum AST typically (although not always) is higher than ALT.
- c Acute hepatitis C may be anti-HCV negative but HCV RNA positive.
- d If anti-HEV IgM positive, consider confirmation with HEV RNA by nested PCR.
- e A liver biopsy is needed to confirm a diagnosis of AIH.
- f If cholestatic injury, magnetic resonance cholangiopancreatography may be recommended.
- g Based on medical history and clinical judgment.
- h Alcohol consumption in past 3 to 5 days.
- i Alcohol consumption in past 3 weeks.

Severity Grade of the Event (Refer to NCI CTCAE applicable version in study protocol for defining the CTC grade/severity)	Dose Modifications	Toxicity Management
Any Grade	Note: It is possible that events with an inflammatory or immune mediated mechanism could occur in nearly all organs, some of them are not noted specifically in these guidelines (eg, immune thrombocytopenia, haemolytic anaemia, uveitis, vasculitis).	
 
The study physician may be contacted for immune-mediated reactions not listed in the "specific immune-mediated reactions" section.
 
Thorough evaluation to rule out any alternative etiology (eg,, disease progression, concomitant medications, and infections).
 
Consultation with relevant specialist.
 
Treat accordingly, as per institutional standard.
 

Grade 1	No dose modifications.	Monitor as clinically indicated
Grade 2	
 
Hold investigational drug(s) until resolution to ≤ Grade 1 or baseline.
 
If toxicity worsens, then treat as Grade 3 or Grade 4.
 
Investigational drug(s) can be resumed once event stabilizes to Grade ≤ 1 after completion of steroid taper.
 
Consider whether investigational drug(s) should be permanently discontinued in Grade 2 events with high likelihood for morbidity and/or mortality when they do not rapidly improve to Grade < 1 upon treatment with systemic steroids and following full taper.
 
	For Grade 2, 3, or 4 Treat accordingly, as per institutional standard, appropriate clinical practice guidelines, and other society guidelines (eg, NCCN, ESMO).
Grade 3	Hold investigational drug(s).	
Grade 4	Permanently discontinue investigational drug(s).	

